
## 4.0 Study Design

This is a multi-centered study being conducted at the following centers:

Fox Chase Cancer Center (FCCC) by the lead investigator, [name], MPH. FCCC will serve as the coordinating center for this study.

CUNY Hunter College under the direction of [name], MPH will conduct community based research initiatives and recruit study participants from the community.

Icahn School of Medicine at Mount Sinai with [name] will obtain IRB approval, recruit subjects and execute the protocol at Mount Sinai.

We will enroll 360 AA smokers, 180 from clinic-based settings in Philadelphia and NYC that serve smokers and 180 from the general community in Philadelphia and NYC. This recruitment strategy will provide a regionally-diverse sample with an increased range of smoking and dependence levels, which will enhance generalizability, as well as power to detect hypothesized genetic effects. To ensure that the demographics of both clinic and community-based samples are balanced, both subgroups will be matched on age and gender.

Subjects that had participated in protocol 14-814, PI [name]'s cohort of cancer-free individuals and indicated they would like to be contacted for possible participation in future research will be offered an opportunity to enroll in this study. These participants will complete the intervention aspect of the study and we anticipate they will help us to reach our recruitment goals. This protocol enrolled subjects in NYC and Philadelphia. It also allowed those enrolled to be notified of other cancer related studies led by [name] and/or her collaborators.

Recruitment and study setting: Philadelphia and NYC are racially diverse, with AAs comprising a large portion of the general populations. This proposed study will leverage on our existing cohort (CAP3) infrastructure, as well as the considerable resources of the Mount Sinai Health System, with which we have partnered to enhance recruitment.

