**Aim 2:** For each SNP, nicotine dependence (as determined by high-very high FTND scores: 6-10) will be modeled using genotype after adjusting for smoking dose (pack-years), age and recruitment setting using logistic regression (LR). Sensitivity, specificity and prediction accuracy (along with 95% confidence bounds) will be used to characterize the precision of binary predictions from LR. Multiple linear regression will be used to correlate the proportion of African ancestry with FTND score (low vs. high) after adjusting for smoking dose, age and recruitment setting. All tests will be two-sided and the Benjamini-Hochberg method will be used to account for multiple testing. Secondary outcomes will include cigarettes per day, age at initiation, and intention to quit. To account for the potentially large number of SNPs resulting from this univariate analysis, penalized logistic regression (PLR) will be used to develop a prediction model for nicotine dependence using these SNPs. PLR has been demonstrated to have excellent power to identify covariate effects as well as superior prediction accuracy compared to competing methods like Classification and Regression Trees and Multifactor Dimensionality Reduction. Sensitivity, specificity and prediction accuracy (along with 95% confidence bounds) will be used to characterize the precision of binary predictions from PLR. AUC curves (along with 95% confidence bounds) will be used to characterize the predictive value of models from these methods. A participant whose predictive probability is  $> 0.5$  will be classified as having high nicotine dependence; however, alternative thresholds will also be evaluated in this

analysis. In addition, the performance of each model will be evaluated using leave-one-out cross validation. All computations will be performed using R statistical language and environment.

**Sample Size and Power:** With 180 subjects each in the low-medium (scores 0-5) and high-very high (scores 6-10) nicotine dependence groups, we will have 80% power to detect a difference in the range of 0.14-0.19 (in minor allele frequency between groups in SNPs of interest) at the 0.005 significance level. This calculation assumes a 10-40% minor allele frequency in the low nicotine dependence group.

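### Aim 2 does not provide for repeating the SNP screen inside cross-validation; followed in the written order, the prediction model's AUC, sensitivity, specificity and accuracy are biased upward

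*Combined protocol and SAP*

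**What the plan says.** All of this is in the Combined protocol and SAP, section 13.0, Aim 2, unless noted.

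- **Screen.** Each SNP is modelled singly by logistic regression against high dependence (FTND 6-10), adjusted for pack-years, age and recruitment setting. On multiplicity: "All tests will be two-sided and the Benjamini-Hochberg method will be used to account for multiple testing". Aims 1 and 3 give an FDR limit of 10%; Aim 2 gives none.
- **Model.** Because many SNPs may come out of the single-SNP step, "penalized logistic regression (PLR) will be used to develop a prediction model for nicotine dependence using these SNPs".
- **Performance.** Sensitivity, specificity, accuracy and AUC are to be reported with 95% bounds. A predicted probability above 0.5 classifies a participant as highly dependent, and "alternative thresholds will also be evaluated".
- **Validation.** As an addition to these measures, "the performance of each model will be evaluated using leave-one-out cross validation".
- **Sample.** Section 4.0 says "We will enroll 360 AA smokers". The Aim 2 power statement uses all of them: "With 180 subjects each in the low-medium (scores 0-5) and high-very high (scores 6-10) nicotine dependence groups". No training/test split and no external sample is named.

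The number of SNPs and the rule for carrying a SNP forward are not given.

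**The concern.** Cross-validation gives an honest estimate only if every step that uses the outcome is redone without the left-out participant. Here the screen uses the outcome. If it is run once on everyone, the SNPs in the model are there partly because they happen to separate these particular 360 people, including the one later left out. The penalty does not cure this, since it shrinks coefficients only after the SNPs have been chosen.

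At stake is whether the Aim 2 prediction results can be believed. A set of SNPs with no predictive value could appear to predict dependence, and the 95% bounds would surround a biased value.

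**Working it through.** **Inputs from the plan:** 180 v 180 participants; two-sided tests; 0.005 per SNP in the power statement; 80% power; reference minor allele frequency (MAF) 10-40%.

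**Assumptions, because the plan is silent:** 100, 200 or 500 SNPs; screen at p<0.05, p<0.005 or Benjamini-Hochberg (BH) 10%; true effects of none, 5 SNPs at odds ratio 1.5, or 30 SNPs at 1.3.

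**Step 1. The plan's own Aim 2 figure.** The plan states "we will have 80% power to detect a difference in the range of 0.14-0.19" in MAF. With n = 180 per group, solve

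d·√n = z(0.9975)·√[2p̄(1−p̄)] + z(0.80)·√[p1(1−p1) + p2(1−p2)], where p2 = p1 + d and p̄ is the mean of p1 and p2.

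- p1 = 0.10: (1.499 + 0.441)/13.416 = 0.145.
- p1 = 0.40: (1.985 + 0.584)/13.416 = 0.191.

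These agree with 0.14-0.19 to rounding. The figure concerns single-SNP tests and says nothing about prediction. The plan gives no expected AUC or accuracy, so there is no stated figure to reproduce for the point itself.

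**Step 2. Null SNPs expected to pass** = number of SNPs × cut-off. At 0.05: 5, 10 and 25 for 100, 200 and 500 SNPs. At 0.005: 0.5, 1.0 and 2.5.

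**Step 3. Simulation with no true effect (true AUC 0.50).** Independent SNPs, MAF 0.10-0.40, ridge logistic regression without covariates, 150 data sets per row. AUC and accuracy come from 20-fold cross-validation averaged over folds, as a stand-in for leave-one-out, because pooled leave-one-out AUC is distorted downward when few SNPs are selected. A separate leave-one-out run gave closely similar accuracy at p<0.05. Results are for data sets in which at least one SNP passed.

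| SNPs | Cut-off | Data sets with a SNP selected | AUC, screen once on all | Accuracy, screen once | AUC, screen in each fold |
|---|---|---|---|---|---|
| 100 | 0.05 | 99% | 0.62 | 59% | 0.50 |
| 200 | 0.05 | 100% | 0.67 | 63% | 0.49 |
| 500 | 0.05 | 100% | 0.76 | 69% | 0.50 |
| 100 | 0.005 | 40% | 0.58 | 57% | 0.53 |
| 200 | 0.005 | 66% | 0.60 | 58% | 0.52 |
| 500 | 0.005 | 93% | 0.62 | 59% | 0.51 |

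The nested values slightly above 0.50 at p<0.005 arise because only data sets in which a SNP passed on the full sample are counted. If data sets with no SNP count as 0.50, the p<0.005 screen-once averages are 0.534, 0.566 and 0.615. Under BH 10%, a SNP passed in only 11%, 5% and 9% of null data sets. The AUC in those was 0.60-0.62, from roughly 8 to 17 data sets per setting.

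**Step 4. Simulation with true effects.** 60 data sets per row, same methods; the last column is screen-once AUC minus AUC in new data.

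| SNPs; true effects | Screen | AUC, screen once | AUC, screen in each fold | AUC in new data | Inflation |
|---|---|---|---|---|---|
| 100; 5 at 1.5 | BH 10% | 0.640 | 0.578 | 0.589 | 0.051 |
| 200; 5 at 1.5 | BH 10% | 0.625 | 0.569 | 0.573 | 0.052 |
| 500; 5 at 1.5 | BH 10% | 0.628 | 0.573 | 0.554 | 0.074 |
| 500; 30 at 1.3 | BH 10% | 0.643 | 0.562 | 0.553 | 0.090 |
| 500; 5 at 1.5 | p<0.005 | 0.671 | 0.570 | 0.566 | 0.105 |
| 500; 30 at 1.3 | p<0.005 | 0.696 | 0.574 | 0.561 | 0.135 |
| 500; 5 at 1.5 | p<0.05 | 0.782 | 0.542 | 0.552 | 0.230 |
| 500; 30 at 1.3 | p<0.05 | 0.804 | 0.579 | 0.580 | 0.224 |

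The BH rows rest on the 48-60% of data sets in which a SNP passed, about 29 to 36 each. Nesting the screen brings the estimate to within about 0.02 of performance in new data in every row.

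**The case against.** **The text does not rule out nesting.** That stands. The plan is silent on where the screen sits, and a reader who inferred that it excludes repeating the screen would go too far. One could even take the model to receive every SNP tested, in which case there is no screen to nest. But the text speaks of SNPs that result from the single-SNP analysis and lists validation last, so the natural reading is one screen on everyone. A prespecified analysis should not leave this open.

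**Only the penalized model is cross-validated.** A reader might infer this, but the plan says otherwise: each model is evaluated, which includes the single-SNP models. The gap concerns the screening step.

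**The inflation is strong.** The documents do not support this as a general statement. The largest values need an unadjusted p<0.05 screen, which the plan never mentions. Its only standards for the SNP tests are BH and, for power, a test "at the 0.005 significance level". Under those the selected set is small and the bias moderate. It does not vanish, as the BH rows show. The plan itself expects that many SNPs may be carried forward, so a looser screen cannot be excluded.

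**Trying several thresholds is a second selection step.** The plan fixes 0.5 and says that alternatives will be looked at; it does not say that the best one will be chosen. AUC does not depend on a threshold. The point arises only if a threshold is picked from the data.

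**The simulation is simplified.** It uses independent SNPs and no covariates, while section 13.0 plans haplotype-block analyses under Aim 1 and covariate adjustment under Aim 2. This limits how exactly the size can be stated, not the direction.

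**Prediction is secondary.** Aim 2 in section 2.0 is about identifying correlated variants, and those tests are untouched. But the plan commits to reporting prediction performance with confidence bounds, so the figures should be sound.

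**Conclusion.** The point holds in this form: the plan does not provide for repeating the SNP screen inside each fold and names no hold-out sample, so the written order yields optimistic AUC, sensitivity, specificity and accuracy.

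The size cannot be fixed from the documents. With an assumed 100-500 SNPs and a true AUC of 0.50, the reported AUC is about 0.62-0.76 for a p<0.05 screen and about 0.58-0.62 for p<0.005 when any SNP passes. Under BH 10% with some true effects, it is about 0.63 against about 0.55 in new data, roughly 0.05-0.10 too high. These figures rest on equal groups of 180, independent SNPs, a ridge penalty and 20-fold cross-validation in place of leave-one-out.

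Because cross-validation is described as an addition, the headline figures might also be in-sample. That is at least as optimistic: in-sample AUC in the null p<0.05 runs was 0.65, 0.71 and 0.82 for 100, 200 and 500 SNPs. The plan does not say which figures will lead.

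The single-SNP association tests and the randomized Aim 3 comparison are unaffected.

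**What to change.** In section 13.0, Aim 2:

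1. State the number of candidate SNPs and the cut-off for carrying a SNP forward, including the FDR limit if BH is the screen.
2. State that the single-SNP screen, the choice of penalty, and the choice of any threshold other than 0.5 that is selected from the data are repeated within every training set, with left-out participants used only for prediction. Say what is predicted when no SNP passes in a fold.
3. Alternatively, drop the screen and give all candidate SNPs to the penalized model, with the penalty tuned inside the loop.
4. Report AUC, sensitivity, specificity and accuracy from these nested predictions as the headline figures, and label any in-sample figures as such. Since pooled leave-one-out AUC is distorted downward when few SNPs are selected, say how AUC is combined over folds.

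The cost is SAP wording and some computing time, with no further participants or data. The downside is that the reported performance will look less favourable.

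### Aim 2 validates its prediction models by leave-one-out; if held-out predictions are pooled, AUC can be biased downward for weak or heavily shrunken models, and stratified 10-fold avoids this cheaply

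*Combined protocol and SAP*

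**What the plan says.** Section 13.0, Aim 2, first fits a logistic model for each SNP, adjusted for pack-years, age and recruitment setting. It then gives the reason for a second stage, "To account for the potentially large number of SNPs resulting from this univariate analysis", and continues that "penalized logistic regression (PLR) will be used to develop a prediction model for nicotine dependence using these SNPs".

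Sensitivity, specificity and accuracy with 95% bounds "will be used to characterize the precision of binary predictions from PLR", and "AUC curves (along with 95% confidence bounds) will be used to characterize the predictive value of models from these methods". A predicted probability above 0.5 is classed as high dependence, with other thresholds also to be examined. The validation statement is that "the performance of each model will be evaluated using leave-one-out cross validation".

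The power paragraph for this aim begins "With 180 subjects each in the low-medium (scores 0-5) and high-very high (scores 6-10) nicotine dependence groups".

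The section does not give the penalty or how it is tuned, the number of Aim 2 SNPs, or whether covariates enter the penalized model. It also does not say whether screening is repeated in each fold, or how held-out predictions are combined into an AUC.

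**The concern.** Leave-one-out gives every participant a prediction from a slightly different fit. The fits differ systematically by outcome: removing a high-dependence participant lowers the training prevalence, and removing a low-dependence participant raises it. A pooled AUC ranks these predictions against each other, so part of the ranking runs backwards. The effect is negligible when the predictors spread people widely. It can dominate when the penalty has shrunk the SNP effects close to zero.

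Weak SNP effects are where honest validation matters most. A weak but real model could be reported as useless, a null model as worse than chance, and the 95% bounds would be centred on the wrong value.

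**Working it through.** **1. The plan's own figure.** Inputs from the Aim 2 power paragraph: 180 per group, 80% power, significance level 0.005 (two-sided), baseline minor allele frequency p = 0.10 to 0.40. With q = p + d, the unpooled formula is d = (2.807 + 0.842) × √{[p(1−p) + q(1−q)]/180}.
- p = 0.10: 3.649 × √[(0.090 + 0.183)/180] = 0.142.
- p = 0.40: 3.649 × √[(0.240 + 0.242)/180] = 0.189.

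The stated 0.14-0.19 is reproduced. The plan states no figure for leave-one-out performance.

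**2. The mechanism at 180/180.**
- Held-out high-dependence participant: training prevalence 179/359 = 0.4986, log-odds ln(179/180) = −0.0056.
- Held-out low-dependence participant: 180/359 = 0.5014, log-odds ln(180/179) = +0.0056.

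The gap is about 0.011 on the logit scale, always in the wrong direction. With all slopes shrunk to zero, every high-dependence participant ranks below every low-dependence one and each falls on the wrong side of 0.5, so pooled AUC and accuracy are both 0.

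In stratified 10-fold, each fold holds out 18 + 18 and the training prevalence is 162/324 = 0.5 every time. In leave-pair-out it is 179/358 = 0.5.

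**3. Size by simulation.** Assumptions: 180/180, allele frequencies uniform on 0.10-0.40, pre-specified SNPs, ridge penalty either fixed or tuned once by 10-fold deviance, 100 replicates. True values come from 20,000 new subjects. Ten-fold AUC is averaged within folds. OR is the per-allele odds ratio. A predictive covariate is one of three covariates, shifted 0.5 SD between classes.

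| Setting | AUC: true / leave-one-out / 10-fold | Accuracy: true / leave-one-out / 10-fold |
|---|---|---|
| 20 null SNPs, tuned | 0.500 / 0.203 / 0.497 | 0.500 / 0.231 / 0.497 |
| 20 SNPs, OR 1.1, tuned | 0.538 / 0.387 / 0.536 | 0.527 / 0.399 / 0.527 |
| 20 SNPs, OR 1.1, penalty 1000 | 0.538 / 0.463 / 0.537 | 0.527 / 0.477 / 0.527 |
| 20 SNPs, OR 1.2, tuned | 0.603 / 0.586 / 0.603 | 0.573 / 0.563 / 0.574 |
| 20 SNPs, OR 1.1, tuned, predictive covariate | 0.618 / 0.605 / 0.616 | 0.584 / 0.579 / 0.583 |
| 20 null SNPs, tuned, predictive covariate | 0.598 / 0.570 / 0.594 | 0.569 / 0.549 / 0.565 |
| 1 null SNP, unpenalized, predictive covariate | 0.629 / 0.616 / 0.626 | 0.592 / 0.585 / 0.588 |
| 1 null SNP, unpenalized, 3 non-predictive covariates | 0.500 / 0.467 / 0.501 | 0.500 / 0.490 / 0.504 |

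The standard error of the leave-one-out AUC bias is 0.022-0.023 in the first two rows and 0.003-0.009 in the rest.

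Other runs show how much the penalty matters. At OR 1.1 with 20 SNPs and penalty 500, leave-one-out gave 0.49 against a true 0.53 (−0.04). Five null SNPs at a nominal penalty of 500 gave 0.26, 0.36 and 0.39 in three separate simulations; predictor scaling may explain the spread. With penalty 1 or 100 and 20 SNPs, one simulation found no downward bias (−0.001 to +0.006), while another found about −0.02 at 100.

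**4. Unequal classes.** At 120/240 the two training prevalences are 119/359 = 0.331 and 120/359 = 0.334, both on the same side of 0.5. Accuracy was then unbiased (0.666 and 0.666), but AUC was not (true 0.531, leave-one-out 0.368; OR 1.1, tuned).

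**5. Screening (200 candidate SNPs assumed).**
- Once on all data at p<0.05: null, true AUC 0.499 against leave-one-out 0.666; 20 causal SNPs at OR 1.1, 0.507 against 0.674, with accuracy 0.505 against 0.630.
- Once on all data with stricter screens (p<0.005 or 10% FDR), weak effects: AUC too low (0.37-0.49 against 0.50-0.52), accuracy too high (0.58-0.60 against 0.50-0.52).
- Repeated inside each fold (p<0.05, 20 replicates): AUC differences −0.022, −0.001 and −0.006, with standard errors 0.024-0.028.

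**The case against.** The strongest reply is that the large figures come from settings the plan need not produce. The single-SNP models carry pack-years, age and setting. The power paragraph also aims at sizeable effects: "we will have 80% power to detect a difference in the range of 0.14-0.19" in allele frequency. With one SNP of that size and three covariates, one shifted 0.3-0.5 SD (an assumption; 25 replicates), true against leave-one-out AUC was 0.655/0.643, 0.690/0.685, 0.666/0.650 and 0.698/0.696. This stands for those models. It is less reassuring for the penalized model, where covariates are not mentioned. Without covariates, three SNPs of the planned size were biased by about −0.05, and a single one fell below 0.5. Even with covariates, one planned SNP plus four null SNPs reached −0.05 at penalty 500.

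Three further limits stand. The 180/180 split is a power assumption: Section 4.0 fixes clinic and community numbers, not dependence groups, so the accuracy part may not apply. The plan does not say that the AUC comes from pooled leave-one-out predictions. The Aim 2 SNP tests and power calculation do not depend on the validation method.

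A reader might infer that leave-one-out will understate performance whatever the model. The documents do not support that. They fix neither the penalty nor the SNP count, and they feed the penalized model with SNPs from a univariate analysis. If that screen is run once on all the data, the net error can be upward.

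**Conclusion.** The concern holds conditionally. If leave-one-out predictions are pooled, AUC can be biased downward, even below 0.5, for weak or heavily shrunken models without predictive covariates. Accuracy at 0.5 can be too when classes are near 1:1. The AUC bias is about −0.01 to −0.03 with a predictive covariate or stronger signal, though heavy shrinkage can exceed that. It is −0.04 to more than −0.13 under strong shrinkage with weak or null effects. The mechanism is exact arithmetic; the sizes depend on assumed SNP counts, effects, penalties and covariates.

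It would also go too far to say that the downward bias survives once screening is nested. The nested check was small and within simulation error, so that is not settled.

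The sponsor cannot know before analysis which case applies, and a less biased method uses the same data. That makes this a recommended cheap improvement, not a must-fix.

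**What to change.** In Section 13.0, Aim 2, replace leave-one-out with repeated stratified 10-fold cross-validation. Compute AUC within each held-out fold and average it, or use leave-pair-out for AUC. State the penalty and its tuning rule, and whether pack-years, age and setting enter the penalized model. Repeat SNP screening, penalty tuning and any choice of alternative threshold inside the training folds.

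In the table, 10-fold AUC was within 0.004 of the true value. That was shown for pre-specified SNPs with a penalty not re-tuned within folds, so it does not by itself demonstrate performance with nested screening.

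The cost is one paragraph of text, a few lines of R, and small Monte Carlo noise from random folds that the repeats reduce. Recruitment and data collection do not change.

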**Intervention Administration:** The intervention will be administered by graduate student trainees. They will be trained to administer the brochure and feedback in a standardized fashion. [name] will train the graduate students in the administration of the hypothetical genetic feedback and the collection of questionnaire data during the post-feedback assessment. The trainees will practice with each other until they achieve proficiency. [name] will also personally observe the first five participant interactions in both NYC and Philadelphia, as well as a random selection of later interactions (n=10) to ensure intervention fidelity. Additional training will be conducted as necessary to ensure fidelity to the intervention.

To address Aim 3, we will administer the following well-established questionnaires, all of which have excellent psychometric properties. The questionnaires are brief, so as not to create undue participant burden. Numeracy, an important predictor of response to risk information, will be assessed using the 7-item Subjective Numeracy scale (SNS), developed by Fagerlin and colleagues. Self-perception of Ancestry Scale (a personal

estimation of the genetic proportion of African ancestors) will be assessed using a measure described and validated by Ruiz-Linares et al.

**Post-Feedback Assessment:** Motivation to quit will be assessed using the Motivation to Quit Smoking Scale (MTSS), which has been found to be a strong predictor of quit attempts. Perceived risk of lung cancer will be assessed using an established face-valid perceived risk scale developed and used by PI [name] in previous work. Cancer worry will be assessed using the well-established 4-item Cancer Worry Scale. Psychological distress will be measured using the BSI-18. For all assessments, participants will be instructed to respond based on how they believe they would feel if they actually received the genetic information that was presented to them.

**Projected Recruitment:** The number of participants that will be enrolled into this study will be 180 for 3 years (approximately 60 patients per year, per site).

Number of subjects per year projected at FCCC	Total number of subjects at FCCC	Number of subjects nationally or internationally (if applicable)	Number of subjects at collaborating institutions (if applicable)
Up to: 60	Up to:180	360	180

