### 13.0 Statistical Analysis

**Aim 1:** Variance stabilizing and normalizing transformations will be applied when appropriate. Descriptive statistics for demographic variables will be presented. The range and mean concentrations of free (NNAL), conjugated (NNAL-Gluc) and total (NNAL+NNAL-Gluc) biomarkers will be summarized by genotype. These concentrations as well as the ratio of NNAL-Gluc:NNAL concentrations will be correlated with each AIM after adjusting for smoking dose (pack-years), age and recruitment setting (clinic vs. community) using analysis of variance. A similar analysis will be done by correlating these variables with each haplotype block. In addition, multiple linear regression will be used to correlate NNAL concentration with proportion of African ancestry after adjusting for smoking dose, age and recruitment setting. To account for multiple testing, the Benjamini-Hochberg (BH) method will be used to control the false discovery rate (FDR). All tests will be two-sided and tests with  $FDR \leq 10\%$  will be considered to be statistically significant.

**Sample Size and Power:** With 360 samples split in a 1:3 ratio between the minor and major allele groups, we will have 80% power to detect an effect size of 0.45 in mean NNAL concentration (total) between the groups using a two-sided test at a significance level of 0.005. This computation is based on a standard deviation of 1 for NNAL concentrations (on the log2-scale) from pilot studies. An effect size of 0.45 corresponds to a 1.37-fold change in NNAL concentration between groups. Similarly, with 360 samples split in a 1:3 ratio between the minor and major allele groups, we will have 80% power to detect an effect size of 1.09 in mean NNAL concentration ratio between the groups using a two-sided test at a significance level of 0.005. This computation is based on a standard deviation of 2.44 for NNAL concentration ratios (on the log2-scale) from pilot studies. An effect size of 1.09 corresponds to a 2.13-fold change in NNAL expression between groups. A significance level of 0.005 results in 1 false discovery per 200 non-differentially expressed SNPs.

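### Aim 2's detectable minor allele frequency difference of 0.14-0.19 is computed on subjects; on alleles, with additive coding, it is about 0.10-0.14, and the sample size is unaffected

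*Combined protocol and SAP*

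**What the plan says.** Everything needed is in section 13.0, Aim 2, of the combined protocol and SAP.

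- Group sizes: "With 180 subjects each in the low-medium (scores 0-5) and high-very high (scores 6-10) nicotine dependence groups".
- Claim: 80% power at the 0.005 level to "detect a difference in the range of 0.14-0.19 (in minor allele frequency between groups in SNPs of interest").
- Baseline: "This calculation assumes a 10-40% minor allele frequency in the low nicotine dependence group".
- Planned test: "nicotine dependence (as determined by high-very high FTND scores: 6-10) will be modeled using genotype" by logistic regression, adjusted for pack-years, age and recruitment setting. Tests are two-sided.

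The section gives no formula. It does not say whether the unit of the power calculation is the subject or the allele, and it does not say whether genotype is coded as additive, dominant or recessive.

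The total of 360 is set in section 4.0: "We will enroll 360 AA smokers, 180 from clinic-based settings in Philadelphia and NYC that serve smokers and 180 from the general community". No section gives an expected distribution of FTND scores.

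**The concern.** Both the difference and the baseline are labelled as minor allele frequencies. Each subject carries two alleles at a SNP, so a MAF estimated in 180 subjects has 360 alleles behind it. The stated range looks too wide for that many observations and looks like a comparison of two proportions with 180 observations each.

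What is at stake is how Aim 2 will be read. The detectable effect tells a reader which SNP effects a null result can rule out. If the figure belongs to a different unit from its label, a null result will be judged against the wrong threshold. Because the genetic coding is not stated, the reader cannot correct the figure or tell in which direction it errs.

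**Working it through.** **Inputs from section 13.0, Aim 2:** 180 subjects per group; two-sided alpha 0.005; power 80%; baseline p1 = 0.10 to 0.40; stated difference 0.14-0.19. **Assumed, not in the documents:** Hardy-Weinberg proportions, no covariate adjustment, no exclusions, higher MAF in the high-dependence group.

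**Formula.** Two proportions, n observations per group, pooled variance under the null:

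n = [z_a √(2 p̄(1−p̄)) + z_b √(p1(1−p1) + p2(1−p2))]² / d²

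with d = p2 − p1, p̄ = (p1 + p2)/2, z_a = 2.807 and z_b = 0.842.

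**Step 1: reproduce the stated figure, one observation per subject (n = 180).**

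- p1 = 0.10, d = 0.1446: (1.499 + 0.441)² / 0.1446² = 180.
- p1 = 0.40, d = 0.1915: (1.985 + 0.584)² / 0.1915² = 180.

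This gives 0.145-0.192, which is the stated range to within rounding. The unpooled formula gives 0.142-0.189 and the arcsine formula 0.142-0.191; both round to 0.14-0.19. The continuity-corrected formula gives 0.151-0.197 and does not fit.

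**Step 2: the same calculation on alleles (n = 360).**

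- p1 = 0.10, d = 0.0964: (1.410 + 0.419)² / 0.0964² = 360.
- p1 = 0.40, d = 0.1354: (1.981 + 0.588)² / 0.1354² = 360.

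This gives 0.096-0.135. The other formulas give 0.096-0.134 (unpooled), 0.095-0.135 (arcsine) and 0.100-0.138 (continuity-corrected). None reaches 0.14-0.19. A simulated additive trend test on 180 + 180 subjects has power 80.4% at 0.0964 and 79.9% at 0.1354.

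**Step 3: power at the stated differences, on alleles.** It is 98.7% for 0.10 vs 0.24 and 99.0% for 0.40 vs 0.59. The simulated trend test gives 98.8% and 99.1%.

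**Step 4: size on the odds ratio scale.**

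| Baseline MAF | On alleles | Implied by the stated difference |
|---|---|---|
| 10% | (0.1964/0.8036)/(0.1/0.9) = 2.20 | (0.24/0.76)/(0.1/0.9) = 2.84 |
| 40% | (0.5354/0.4646)/(0.4/0.6) = 1.73 | (0.59/0.41)/(0.4/0.6) = 2.16 |

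**Step 5: would another coding explain the figure?** Here each subject is one binary observation, n = 180, and the stated MAF is converted to the genotype-group proportion.

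| Coding | Baseline proportion at MAF 10% / 40% | Detectable difference in that proportion | Same, as a MAF difference |
|---|---|---|---|
| Dominant (carriers), 1−(1−MAF)² | 0.19 / 0.64 | 0.171 / 0.171, peak 0.191 between | 0.10 / 0.17 |
| Recessive, MAF² | 0.01 / 0.16 | 0.086 / 0.164 | 0.21 / 0.17 |

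Neither coding gives 0.14 rising to 0.19 from a 10-40% MAF.

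**Step 6: dependence on the even FTND split.** Allele-based range and power with the total held at 360 subjects; the shares below 50% are illustrative.

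| Share with high dependence | Low/high subjects | Detectable MAF difference | Power at 0.14 / 0.19 |
|---|---|---|---|
| 50% | 180/180 | 0.096-0.135 | 98.7% / 99.0% |
| 40% | 216/144 | 0.097-0.138 | 98.4% / 98.7% |
| 30% | 252/108 | 0.103-0.147 | 97.0% / 97.2% |
| 20% | 288/72 | 0.117-0.168 | 91.9% / 90.6% |

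**The case against.** The strongest defence is that no sum is wrong. The figure follows from the stated n, alpha, power and baseline, and only the word allele is out of place. The Aim 1 power paragraph splits samples into minor and major allele groups, so Aim 2 may use the same shorthand for groups of subjects. That plausibly explains the slip but does not remove it: Aim 2 labels both the difference and the baseline as MAF, and under that label the figure is not the detectable difference. If subjects were meant, both numbers need relabelling.

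A second defence is that nothing depends on the figure. A reader might infer from a faulty power statement that Aim 2 is underpowered or that 360 is wrong. The documents do not support that: 360 is set by the recruitment plan, and for additive coding the stated figure understates the study's sensitivity. Nor can one call the figure conservative without qualification, since under recessive coding at 10% MAF about 0.21 is needed against the stated 0.14.

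A third objection stands in full. The range 0.10-0.14 is a best case: the planned model adjusts for covariates, and section 4.2 excludes low-DNA samples and incomplete questionnaires. If these together inflated the variance by an assumed factor of 1.1, 1.25 or 1.5, the range would be 0.102-0.142, 0.110-0.151 or 0.122-0.166. The restated figure must carry that caveat.

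Finally, a reader might infer that 180 per dependence group was borrowed by mistake from the 180/180 recruitment quotas by setting (section 4.0) or by site (section 4.1). The documents do not show this. The split is worded as a premise of the calculation; what is missing is any FTND distribution to support it.

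**Conclusion.** The concern holds as a mismatch between figure and label. As a MAF difference for an unadjusted additive test, 80% power is reached at 0.096-0.135, not 0.14-0.19, and the stated differences have about 99% power. In odds ratio terms the plan can detect 2.20 and 1.73 per allele at the two ends of the baseline range, where its figures imply 2.84 and 2.16. None of the three usual codings makes the stated difference, label and baseline agree.

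This rests on Hardy-Weinberg proportions, an even FTND split, and no allowance for covariates or exclusions. That the calculation was done on subjects is inferred from the reproduction; the document does not state the unit. The direction of the error depends on the coding: conservative for additive, optimistic for recessive at low MAF. The consequence is confined to how Aim 2's sensitivity is described and how a null result is interpreted. The design and sample size stand.

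**What to change.** In the Aim 2 power paragraph:

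1. State the genetic coding used in the per-SNP logistic regression and the unit of the power calculation.
2. Either restate the detectable MAF difference as about 0.10-0.14 (additive coding, 360 alleles per group, before covariate adjustment and exclusions), or give both the difference and the baseline as proportions of subjects in a named genotype group. For carriers, that is 0.17-0.19 at a baseline of 19-64%.
3. Say that the figure assumes an even split on FTND, and show the range for less even splits, for example 0.097-0.138, 0.103-0.147 and 0.117-0.168 at an assumed 40%, 30% and 20% high dependence.

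The cost is a few sentences. No participants, data or analyses are added. The one drawback is that 0.10-0.14 looks more favourable than the present figure, so its conditions need to be printed beside it.
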